17.0 Appendix

Attachment 1: Concomitant Medication Table

Medication	Allowed	Notes
Amitriptyline	No	
Amphetamines et., methylphenidate, dextroamphetamine)	No	
Antiemetics (eg., metoclopramide, domperidone, others with dopamine blocking properties)	No	
Antiepileptic mood stabilizers	Yes	Stable dose, no changes or additions
Antihistamines, nonsedating (eg., loratadine, fexofenadine, cetirizine)	Yes	
Antihistamines, sedating (eg., diphenhydramine, hydroxyzine, meclizine, benz tropine)	Yes-Episodic Use Only	No use within 24 hours of cognitive assessments
Antipsychotic medications	Yes	Stable dose over four weeks prior to randomization, no changes or additions during duration of trial
Barbiturates	No	
Benzodiazepines	Yes-Episodic Use Only	No use within 24 hours of cognitive assessments
Chlorpromazine	No	
Bupropion	No	
Clozapine	No	
Decongestants (eg., pseudophedrine)	Yes-episodic use only	No use within 24 hours of cognitive assessments
Doxepine	No	
Dicyclomine	No	
Herbal medications or Over the Counter Medications w/ primary CNS activity	No	
Lithium	Yes	
MAOIs	Yes	
Methadone	No	
Mirtazepine	Yes	Stable dose, no changes or additions

Muscle Relaxants	Yes-Episodic Use Only	No use within 24 hours of cognitive assessments
Nicotine Replacement	Yes	
Nortriptyline	No	
Opiates	No	
Benzodiazepine derivative sleep agents (eg., Zolpidem)	Yes-Episodic Use Only	No use within 24 hours of cognitive assessments
SNRIs	Yes	
SSRIs	Yes	
Tricyclic antidepressants	Yes	
Trazodone	Yes-Episodic Use Only

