4.0 Eligibility Criteria

Inclusion criteria:

1. Overtly healthy men and women aged 21 – 35
2. Able to give informed consent
3. Able to understand/complete questionnaires and procedures in English
4. Willing and able to adhere to the study schedule
5. At least 2 binge drinking events (at least 4 or 5 drinks on a drinking day for women and men respectively over the last 5 weeks, unless determined by study physicians that drinking history meets study objectives
6. Have venous access sufficient to allow blood sampling

Exclusion criteria:

1. Pregnant or breast-feeding
2. Desire to be treated for any substance use disorder or court ordered to not drink alcohol
3. Medical disorders or other conditions, such as lifetime history of a seizure, including history of ECT but excluding febrile seizures and those induced by substance withdrawal, that may influence study outcome or subject safety
4. First degree relative with idiopathic epilepsy or other seizure disorder
5. DSM 5 Disorders (non-AUD) or current/history of neurological disease of cerebral origin, or head injury with > 20 min loss of consciousness, if determined by the study physicians to affect subject safety or data integrity

6. Positive urine drug screen for amphetamines/ methamphetamines, barbiturates, benzodiazepines, cocaine, opiates, or phencyclidine if determined by the study physicians to adversely affect subject safety or data integrity
7. Medications (past 30 days) that could influence subject data/subject safety (e.g. antidepressants, antipsychotics, benzodiazepines, etc.) as determined by study physicians
8. Positive BrAC reading at beginning of any study session
9. Actively suicidal (for example, any suicide attempts within the past 3 months or any current suicidal intent, including a plan) or are at serious suicidal risk, by clinical judgment of the study physicians
10. Any condition for which the study physicians determine it is unsafe or not prudent to enroll a subject

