5.0 Study Design

This will be a single site randomized, 2-session, within-subject cross-over design pilot study (Figure 2). 20 enrolled (of 30 consented) subjects reporting varying levels of binge and high intensity drinking, defined as at least 2 episodes of drinking 4 (for women) or 5 (for men) drinks on an occasion over the last 5 weeks, (unless determined by PI that drinking history meets study objectives), will be enrolled. Subjects will be randomized to undergo one session of rTMS or sham immediately followed by our rate control IV ASA paradigm. Subjects will then return 7-14 days later and undergo the same sequence of events with the opposite intervention (i.e. rTMS or sham) from session 1.

Duration of Treatment

Subjects will complete two stimulation (LF and sham) and IV ASA paradigm sessions over two to three weeks, with one session occurring every 7-14 days. Previous work has demonstrated that a single session of rTMS is sufficient to modulate AUD related behavior³⁰.

Clinical Research Sites

rTMS treatments and alcohol challenge sessions and lab visits will take place at the Indiana Clinical Research Center, in either Goodman Hall at the Neuroscience Center and/or in the Neural Systems Laboratory at Indiana University Hospital.

[name] is the Medical Director of the IU Neurostimulation Program and is a psychiatrist in the IU Department of Psychiatry. [name] and associated research personnel will conduct TMS procedures, help with subject transportation and monitoring, and assist with gathering demographic data. The program has 1 research psychiatrist and 1 research coordinator.

[figure not shown]

Figure 2: Study Design for rTMS Modulation of ASA

[name] is the Research Medical Director of the IU Psychotic Disorders Program (IUPDP). The IUPDP is located in Indianapolis, IN. and is part of the IU Department of Psychiatry. IUPDP research personnel will conduct TMS procedures, help with subject transportation and monitoring, and assist with gathering demographic data. The IUPDP has 2 research psychiatrists, a fully dedicated study manager, a fully dedicated study coordinator, one dedicated subject recruiter, and two raters (1 PhD, 1 Masters level) who have been trained and have extensive experience in conducting the assessments and cognitive tests used as outcome measures.

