7.0 Study Procedures

Recruitment and Screening

Subjects from the NSL registry will be contacted by phone or email, while other subjects will contact the study phone line or email after learning about the study from print, electronic advertising, or word of mouth. Subjects who meet basic criteria will either 1) be invited for an in-person interview when they will consent to participate in the study, or 2) arrange for a remote interview where they will consent to participate and complete interview measures electronically and converse with study staff via IU Zoom Health or similar secure platform. Subjects will complete some or all of the following measures, at the discretion of the principal investigators:

Self-Report Measures:

- The Alcohol Use Disorders Identification Test (AUDIT)
- The Family History of Alcoholism Module of the SSAGA
- The UPPS-P Impulsive Behaviors Scale measures impulsivity traits
- Self-Rating of Effect of Alcohol assessing retrospective sensitivity to the subjective response to alcohol (SRE).
- Short Inventory of Problems – Revised (SIP-r)
- Medical History (including menstrual phase for women)

- Nicotine History Measure
- Penn Alcohol Craving Scale (PACS)
- Subjective Response Questions
- Five Factor Model Form
- Drinking Refusal Self-Efficacy Questionnaire-Revised (DRSEQ-R)
- Alcohol Expectancy Questionnaire (Full and Brief versions)
- Drinking Motives Questionnaire (Full and Brief versions)
- COVID-19 Questionnaire

Interviews:

- The Semi-structured Assessment for the Genetics of Alcoholism – II, Alcohol

Diary Measures:

- Timeline Follow-back (TLFB) modified to assess for one-month recall of alcohol, tobacco, drug, and cannabis use

Screening tools:

- Clinical Institute Withdrawal Assessment for Alcohol Scale (CIWA)
- GAD-7 and GAD-2 Generalized Anxiety Disorder Assessment, 7 and 2 item scales assessing anxiety symptoms over the last 2 weeks
- PHQ-9 and PHQ-2 Patient Health Questionnaire, 9 and 2 item scales assessing depressive symptoms over the last 2 weeks
- Urine pregnancy and drug screen (UPS, UDS, including EtG urine screen at discretion of study physicians)
- Breath Alcohol Concentration Measurement
- Liver function assessment
- TMS Screening Checklist

Miscellaneous:

- Contact Form and Follow-up questionnaires

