Note: Screening tool score above the cutoff or concerning patterns as determined by the study technician may prompt additional testing from the set of measures completed at the interview (For example, PHQ-2 score greater than or equal to the cutoff of 3 will prompt completion of the PHQ-9.).

Subjects that complete part of the interview remotely and appear to meet study criteria will be asked to visit the ICRC for a short visit where they will provide a blood sample, urine, and be paid the interview fee of \$25. Blood samples may be stored indefinitely in a secure location for future genetic research. There is not a plan to submit to the NIH genomic database. At this time, there is no planned analysis for these samples and due to our sample size, we do not meet the requirements for inclusion in the NIH genomic database. Subjects who complete part of the interview remotely and do not meet study criteria will be informed of the decision and mailed a check or gift card in the amount of \$25.

Based on the information collected at the screening interview, the investigators will decide whether or not to enroll the subject in the study. If the subject is enrolled in the

study, they will be either randomly assigned to one of the two schedules, or assigned to one of the two schedules based on group enrollment balance or subject safety at the discretion of the study physicians, and contacted to schedule their experimental sessions. If the subject agrees to enroll in the study and schedules their study visits, they will be sent an email with pertinent information.

Procedures on the testing day

Orientation to Laboratory: On the days of testing, the subject will arrive at the ICRC between 7:00 and 9:00 am and undergo a brief physical exam by ICRC Nurses, testing of urine for hCG in females and a drug screen for all subjects, and documentation of zero BrAC before a 550 cal breakfast is served. *Study protocol will be reviewed and car keys, if the subject drove themselves, taken for safekeeping or confirmed that the keys are held by the hospital valet service.* Age, sex, blood pressure, heart rate, temperature, height, and weight will be measured.

rTMS Treatment

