Using individualized PBPK parameters⁴⁴, the Computer-assisted Alcohol Infusion Software⁴⁵⁻⁴⁸ will deliver an approximately 6.0 % (v/v) alcohol solution prepared by the Research Pharmacy. The infusion rate profile is based on individualized physiologically-based pharmacokinetic model parameters to achieve specified incremental alcohol exposure rates independent of the subject's age, height weight and gender. The safety limit will be set to 170 mg/dL, but subject inputs that would exceed 165 mg/dL are

disabled, allowing subjects to self-administer to a high-intensity drinking threshold of 160 mg/dL if they so choose and accommodating potential deviance from our pharmacokinetic modelling or measurement error.

We will use the rate control paradigm during the 90-minute alcohol self-administration session to allow the subject to determine their alcohol exposure trajectory (Figure 3). For the first self-administration epoch and at the end of each subsequent 3-5 min self-administration interval, the subject will specify the next alcohol exposure rate. Alcohol delivery raises the subject's BrAC by the specified rate over 3-5 minutes. During the last ~0.5 minutes of the exposure, the subject may complete the brief computer-assisted assay of craving for alcohol and subjective response and then select the next exposure rate, all while the current exposure rate is maintained.

[figure not shown]

Figure 3: Exposure Rate Selection and Subjective Response Determination Sequence. The task begins with an initial exposure rate selection, with the display indicating no past rate of change (baseline). After 2.5 minutes, a set of subjective responses are collected over approximately 20 sec after which time the next exposure rate selection prompt is displayed, now indicating the prior selection in the left hand (shaded) portion of the display. The choice and subjective response sequence is repeated throughout the experiment. The next exposure rate is then selected by rotation of the CAIS response button (Griffin Technologies Powermate®, inset) to a position within the available range depicted in gray. The arrow position follows button rotation in real time, and rate chosen by single button press. Text instructions are for illustrative purposes.

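### The 24-hour medication limit is tied to cognitive assessments that the trial does not schedule, so no drug-free interval applies before the rTMS and IV alcohol sessions

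*Combined protocol and SAP*

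**What the plan says.** The concomitant medication table (Section 17.0, Attachment 1) marks five drug classes as allowed for episodic use only and attaches the same note to each: "No use within 24 hours of cognitive assessments". The classes are sedating antihistamines, benzodiazepines, decongestants, muscle relaxants and benzodiazepine-derivative sleep agents. The same table allows antipsychotics at a stable dose, and it allows SSRIs, SNRIs, MAOIs and tricyclics.

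Section 4.0 approaches medication from the other side. Exclusion 7 reads "Medications (past 30 days) that could influence subject data/subject safety (e.g. antidepressants, antipsychotics, benzodiazepines, etc.) as determined by study physicians". Exclusion 6 covers a "Positive urine drug screen for amphetamines/ methamphetamines, barbiturates, benzodiazepines, cocaine, opiates, or phencyclidine", again subject to the study physicians' judgement. Exclusion 8 is worded to apply at every visit: "Positive BrAC reading at beginning of any study session". Exclusion 7 has no such wording.

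On each testing day Section 7.0 provides for "testing of urine for hCG in females and a drug screen for all subjects". The infusion software then disables "subject inputs that would exceed 165 mg/dL", so self-administration up to that level is possible.

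**The concern.** A timing restriction works only if the event it refers to takes place. Here that event is a cognitive assessment, and the trial appears to have none. The five classes would then have no operative drug-free interval before the two procedures that matter, rTMS and IV alcohol.

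Two things are at stake. The first is safety: a participant could comply with the table, take a permitted sedating drug the evening before a session, and then receive IV alcohol. The second is the crossover comparison. A stable-dose drug is present at both sessions and largely cancels within subject. A drug taken before one session and not the other does not cancel, and the primary outcome is how quickly the participant chooses to reach 80 mg/dL.

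A further difficulty is that a physician exercising the discretion in exclusion 7 finds the criterion pointing one way and the table the other.

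**Working it through.** The plan gives no figure to reproduce on this point. The check is a count and a comparison of sections.

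**1. Rows that carry the note.** Attachment 1 has 29 legible rows; the text breaks off at trazodone. Six rows allow episodic use only. Five of them carry the 24-hour note. The sixth, trazodone, shows no note in the available text and is not counted.

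**2. Is a cognitive assessment scheduled?**

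| Where | What is listed | Cognitive assessments |
|---|---|---|
| Section 3.0, outcomes | Time to 80 mg/dL; subjective responses; TLFB drinking | 0 |
| Section 7.0, procedures | Questionnaires, interviews, screening tools, rTMS, alcohol infusion, follow-up | 0 |
| Section 9.0, calendar, all rows | 31 rows | 0 |
| Section 9.0, rows marked at the experimental visits | TLFB, UDS, UPS, BrAC, rTMS, Alcohol Exposure, Subjective Measures (7 rows) | 0 |

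Section 5.0 does mention staff experienced in "conducting the assessments and cognitive tests used as outcome measures". That phrase describes a collaborating program's raters. It names no test and no visit, and Section 3.0 lists no cognitive outcome. It therefore does not give the 24-hour note anything to attach to.

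**3. Does another provision supply the interval?**

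- *Exclusion 7* looks back 30 days, but it is an eligibility criterion at physician discretion, and the text does not say it is applied again at session 2, which falls 7 to 14 days after session 1.
- *Exclusion 6 with the session-day urine screen.* The list has 6 entries: amphetamines/methamphetamines, barbiturates, benzodiazepines, cocaine, opiates and phencyclidine. Its overlap with the five restricted rows is 1, benzodiazepines. Sedating antihistamines, decongestants and muscle relaxants are not on the list, and sleep agents such as zolpidem are not named.
- *Exclusion 10* is a general judgement about enrolment and gives no interval.

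No provision states a medication-free period before a session.

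**4. Table against exclusion 7.**

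| Example in exclusion 7 | Status in Attachment 1 |
|---|---|
| Antidepressants | MAOIs, SNRIs, SSRIs, tricyclics: yes; mirtazapine: yes at stable dose; trazodone: episodic (6 rows) |
| Antipsychotics | Yes, at stable dose (1 row) |
| Benzodiazepines | Episodic use (1 row) |

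All 3 of the 3 examples are allowed in some form. Some individual agents are barred: amitriptyline, nortriptyline, doxepin, bupropion, clozapine and chlorpromazine.

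**5. Would discordant use be recorded?** Medical History is marked at the interview only, and no calendar row is a dedicated concomitant-medication record. The TLFB is scheduled at both sessions and is "modified to assess for one-month recall of alcohol, tobacco, drug, and cannabis use". Whether drug use there includes prescribed or over-the-counter medicines is not stated.

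**6. Scale.** Section 12.0 expects 20 × (1 − 0.30) = 14 completers. One participant with discordant use would be 1/14, about 7% of the analysed sample. The documents do not allow an estimate of how many there would be.

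**The case against.** The strongest reply is that the table does not act alone. A participant must first pass exclusion 7, whose 30-day look-back is much longer than 24 hours, which names benzodiazepines and whose list is open-ended. The visible body text never says that Attachment 1 overrides it, and does not refer to the attachment at all. Session days include a nurse's physical exam, a urine screen, monitoring by medically trained staff during rTMS, breath alcohol sampling and prolonged observation afterwards, and the investigator can end participation. The table bars herbal and over-the-counter products with primary CNS activity. Sequence is randomized and counterbalanced and subjects are blinded, so sporadic use has no stated reason to favour either condition. On this view a few words in an appendix need correcting and little more.

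Much of this stands as a limit on the size of the point. The expected effect on the comparison is mainly noise, not systematic bias. Participants are healthy and aged 21 to 35, so use of the permitted psychotropics may be uncommon. Decongestants do not fit the sedation argument. The TLFB may capture some medication use. What the urine assay detects is not stated, so sleep agents might be covered in practice.

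None of it supplies a drug-free interval. Exclusion 7 is discretionary and not tied to session days. Monitoring and the power to stop can respond to a reaction but do not prevent co-exposure. The over-the-counter row is offset by the row that names diphenhydramine as allowed episodically. If the table does not govern, then no pre-session interval is stated anywhere in the documents.

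**Conclusion.** The concern holds. The only timing rule for five permitted drug classes refers to an event that is not in the trial, so it has no effect, and nothing else sets an interval before rTMS or IV alcohol. The existing screen and physician discretion close the gap in part, with one of the five classes named in exclusion 6.

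The overlap with exclusion 7 is real for all three of its examples, but it is unclear guidance and not two absolute rules in conflict.

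The conclusion rests on reading the note literally and on the legible part of the table. The consequence for time to 80 mg/dL cannot be quantified from the documents. This should be fixed, chiefly for participant safety and to limit discordant exposure between sessions; it does not invalidate the trial.

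**What to change.** - Reword the note in the five rows so that use is barred within 24 hours of each rTMS/alcohol session, or within a longer interval set by the study physicians. The documents give no basis for choosing a specific longer washout. This change alone resolves the main defect.
- Align the table's entries for antidepressants, antipsychotics and benzodiazepines with exclusion 7, and state whether that criterion is re-checked at each session, as exclusion 8 already is.
- Ask about prescribed and over-the-counter medication at both sessions, for instance as an item added to the TLFB already scheduled there, so that discordant use can be identified.

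The cost is a small amendment to one table and one criterion, one extra question per session, and an occasional rescheduled session. There is no statistical cost.
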